4.2. Sample Size and Power

A total evaluable sample size of 36 subjects, (24 ALXN1210 SC subjects [receiving active treatment] from Cohort 1 and 12 ALXN1210 IV subjects from Cohort 2), will provide > 80% power to infer that the lower bound of a 90% confidence interval (CI) for the ratio of the bioavailability of ALXN1210 SC to IV is > 0.4, assuming an absolute bioavailability of 0.6 and a coefficient of variation (CV) of 0.35. Additionally, 6 subjects will receive placebo treatment via the SC route, including 2 in Cohort 1a and 4 in Cohort 1b. Randomization within Cohort 1a (6 subjects) will be conducted in a 2:1 ratio. After Cohort 1a, 36 subjects will be randomized in a 2:1 ratio to Cohort 1b (ALXN1210 SC or placebo SC) or Cohort 2 (ALXN1210 IV), and within Cohort 1b, subjects will be randomized in a 5:1 ratio, to receive either ALXN1210 SC or ALXN1210 SC placebo. This brings the total planned number of subjects to N = 42.

4.3. Demographics, Baseline Characteristics, and Subject Disposition

All subjects will be included in the summary of subject disposition. This will present the overall number of subjects screened and by treatment group and overall the frequency and percentage of subjects randomized and treated, and who completed or discontinued from the study, along with reason for discontinuation. Furthermore, the number and percentage of subjects in each study population will be tabulated. Non-eligible and discontinued subjects will be listed. Subject assignment to study populations will be listed. Demographics and baseline characteristics (including height, body weight and body mass index) will be listed and summarized by each treatment group and overall for the safety population. If the remaining populations are different from the safety population, separate demographic tables will be produced.

4.4. Safety Analysis

Safety analyses will be performed on the safety population, and will be reported by each treatment group and overall. Safety analyses will include an analysis of all

Statistical Analysis Plan

AEs, ECGs, clinical laboratory data, vital sign measurements, and physical examination results and will be presented using descriptive statistics. No inferential statistical analyses are planned on the safety parameters of this study.

Adverse Events

The incidence of treatment-emergent (after dosing) AEs (TEAEs) will be summarized using the safety population. The Medical Dictionary for Regulatory Activities (MedDRA) dictionary Version 19.0 (or higher) will be used to classify all AEs reported during the study by System Organ Class (SOC) and Preferred Term. A summary of TEAEs including the incidence of subjects who experienced TEAEs (number and percentage of subjects) and incidence of TEAEs (number of events) will be presented for each treatment group and overall, by severity and by relationship to study drug. TEAEs and serious TEAEs will be summarized by SOC and Preferred Term for each treatment group and overall, by severity, and by relationship to study drug. Treatment group will be categorized by the treatment that was actually received at the date of AE onset (i.e., ALXN1210 SC, ALXN1210 IV or ALXN1210 placebo SC). Subjects having multiple AEs within a category (e.g., overall, SOC and Preferred Term) will be counted once in that category. For severity tables, a subject's most severe event within a category will be counted. For relationship tables, a subject's event with greatest relationship to study drug within a category will be counted. In each table, SOC and Preferred Term will be presented in descending order of overall incidence rate (alphabetical order will be used in case of equal rates). All TEAEs, serious TEAEs, TEAEs resulting in withdrawal from the study, TEAEs occuring during study drug administration and AEs that occurred before first dose administration will be presented in by-subject listings.

Medical History

Medical history data will be coded using MedDRA dictionary Version 19.0 (or higher) and listed individually.

Vaccination Status

A listing of MCV4 and Serogroup B vaccination status and dates will be presented individually.

Study Drug Administration

Study drug administration data will be listed individually.

Vital Signs

Vital signs data (systolic and diastolic blood pressure, heart rate, temperature, and respiration rate) will be listed for individual subjects. In addition, height and body weight will be listed for individual subjects. Summary statistics of absolute (observed) values and changes from Baseline will be calculated for each parameter by each treatment group.

Laboratory Data

Clinical laboratory parameters (blood chemistry, hematology, coagulation, urine chemistry, urinalysis and other laboratory results) will be listed and abnormal parameters will be flagged as high (H) or low (L) according to reference ranges. Absolute (observed) values and changes from Baseline (continuous variables) will

Statistical Analysis Plan

be summarized by each treatment group based on scheduled values. The first scheduled lab value will be used for summary analysis if repeated measurements are made at any time point.

For summary statistics, a lab value with "<" will be replaced with a numeric value by removing the "<" sign. In the listings, the values will be displayed as originally reported by the laboratory.

Laboratory parameter values will be graded according to the Common Terminology Criteria for Adverse Events (CTCAE). Parameters that are not present in this document will be omitted. Shift tables by treatment group will be produced for these laboratory parameters by grade. These tables will summarize the number of subjects with each baseline grade relative to the normal ranges and changes to the worst highest grade assessed post-dose during the study.

Electrocardiograms

Electrocardiogram parameters will be measured at the specified time points and will include heart rate, PR, RR, QRS, QT, and corrected QT interval corrected using Fridericia's formula (QTcF)(QTcF=QT/RR^1/3) intervals and will be listed individually. The average of the ECG readings at the time points collected will be calculated, and absolute (observed) values and changes from Baseline values will be summarized by each treatment group.

An outlier analysis will be performed that will summarize the frequency and percentage of subjects who meet any of the following outlier criteria at each visit by treatment group:

- QT, QTcF interval > 450 msec
- QT, QTcF interval > 480 msec
- QT, QTcF interval > 500 msec
- QT, QTcF interval increases from baseline > 30 msec
- QT, QTcF interval increases from baseline > 60 msec

Prior and Concomitant Medications

All prior and concomitant medications will be coded using the World Health Organization (WHO) Drug Dictionary version June 1, 2016 and will be listed individually. The frequency and percentage of prior and concomitant medications will be summarized by Anatomical Therapeutic Chemical (ATC) and Preferred Name. Separate tables will be given for prior and concomitant medications. Prior medications are defined as those for which the end date is prior to the date of first study drug administration. Concomitant medications are defined as those with start date on or after the date of first study drug administration and those with start date prior to the first study drug administration but with end date on or after the date of first study drug administration. Non-pharmacologic therapies and procedures and prophylactic antibiotic treatment will be listed.

Physical Examination

Physical examination data will be listed.

Statistical Analysis Plan

Infusion/Injection Site Evaluation

Data from the injection/infusion site evaluations will be listed individually.

Visual Assessment Scale for Pain at Infusion/Injection Site

Data from the pain at infusion/injection site will be listed individually.

4.5 Pharmacokinetic Analysis

All serum concentration data will be listed for each individual subject and summarized at each time point by treatment group for ALXN1210-treated subjects.

If a Below the Level of Quantitation (BLQ) value occurs in a profile before the first measurable concentration, it will be assigned a value of zero concentration. If a BLQ value occurs after a measurable concentration in a profile and is followed by a value above the Lower Level of Quantitation (LLQ), then the BLQ will be omitted following visual inspection of the serum concentration versus time profile to assess the appropriateness of this assignment. If a BLQ value occurs at the end of a collection profile (after the last quantifiable concentration), the value will be treated as missing data. If 2 BLQ values occur in succession, the profile will be deemed to have terminated at the first BLQ value and any subsequent concentrations will be omitted from PK calculations.

Samples with no reportable value due to a bioanalytical issue or missing samples will be set to missing, and will not be included in the PK calculations.

When calculating the mean or median value for a concentration at a given time point, all BLQ values will be set to zero except when an individual BLQ falls between 2 quantifiable values, in which case it will be omitted.

For tabulation, graphical representation, and calculation purposes, all samples with no reportable value (or missing samples) observed after dosing will be set to missing.

Individual and mean concentrations versus nominal time on linear and semi-log scales will be presented graphically.

Individual serum concentration data for ALXN1210-treated subjects, with actual sampling dates and times calculated relative to the start of the infusion/injection, will be used to derive the PK parameters by non-compartmental analyses using Phoenix WinNonlin Version 6.3 or higher.

The following PK parameters will be derived:

Maximum observed serum concentration (C_{max})

- Time to maximum observed serum concentration (T_{max})
- Area under the serum concentration versus time curve from time zero to the last quantifiable concentration (AUC_t)
- Area under the curve from time zero to infinity (AUC_{∞})
- Terminal elimination rate constant (λ_z)
 - Only those data points that are judged to describe the terminal loglinear decline will be used in the regression.

Page 10 of 13

- $\circ~$ A minimum number of 3 data points in the terminal phase will be used in calculating λ_z , with the line of regression starting at any post-C_{max} data point (C_{max} should not be part of the regression slope)
- Terminal elimination half-life $(t_{\frac{1}{2}})$
- Total clearance (CL or CL/F), calculated as dose/AUC $_{\infty}$
- Apparent volume of distribution during terminal phase (V_d or V_d/F), calculated as dose/($\lambda_z*AUC_\infty)$

All pharmacokinetic parameters will be listed for each individual subject and will be summarized by treatment group. In addition, 95% CI of the mean and geometric mean parameters will be calculated.

Some PK parameters may not be calculated for all or some subjects if the concentration data are not deemed to be amenable to evaluation. Explanations for PK parameters that could not be estimated will be provided in the clinical study report (CSR).

Additional PK parameters may be calculated, as appropriate.

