¹ Permissible windows for study assessments are described in the study operations manual. ² EOI will be approximately 15 minutes after SOI.

³ Subject will be discharged from CRU after completing all Day 5 assessments. Subjects will be provided a "Study Participant ID card" with information for Healthcare Provider and participant on symptoms of meningitis infection.

⁴ Signed and dated EC-approved ICF must be obtained before any study-specific screening procedures are performed.

⁵ For subjects who do not have adequate documentation of prior MCV4 immunization or serogroup B vaccination, MCV4 immunization will be performed at least 56 days prior to first dose on Day 1, and vaccination for serogroup B meningococcal infections will be administered at least 56 days prior to Day 1 dosing with a booster administered at least 28 days prior to dosing on Day 1.

⁶ Complement activity, confirmed by a suitable assay such as complement alternative pathway (CAP) ELISA/C5 (hemolysis) inhibition, will be performed at screening to confirm subjects do not have a complement deficiency.

⁷ The sample drawn on Day -1 will be stored for future analysis should the post-dose sample indicate that complement has not normalized.

⁸ Serum pregnancy test for all female subjects to confirm a female subject is not pregnant.

⁹ On Dav 1, vital sign measurements will be assessed pre-dose (within 15 minutes prior to SOI) and at EOI, 30 minutes after EOI, 2 hours after SOI, 4 hours after SOI, and 8 hours after SOI.

¹⁰On Day 1, triplicate 12-lead ECGs will be performed pre-dose and approximately 15 minutes post-EOI.

¹¹Continuous cardiac registration predose through duration of IV infusion (Cohort 2) and until 3 hours post SC injection (Cohorts 1a and 1b).

¹²Infusion or injection site evaluations will be done within 15 minutes of the start of infusion/injection and \pm 15 minutes of the other scheduled times on Day 1. Indurations or reactions < 1cm will not be listed as an adverse event unless it persists for more than 24 hr. Pain at site of infusion or injection will be assessed using a Visual Analog Scale (0-10). Pain will not be assessed pre-dose.

¹³The investigator or designee will meet with the subject at each visit to discuss the potential safety risks of ALXN1210, and to address any safety concerns on the part of the subject.

¹⁴Collection of AEs and SAEs will begin at ICF signing.

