- 9. Positive or indeterminate QuantiFERON[®]-TB test indicating possible tuberculosis (TB) infection.
- 10. History of latent or active TB or exposure to endemic areas within 8 weeks prior to the screening visit.
- 11. Female subjects who are breastfeeding or are heterosexually active and unwilling to practice contraception and are not postmenopausal. Postmenopausal is defined as amenorrhea ≥ 12 consecutive months without another cause and a documented serum follicle-stimulating hormone level ≥ 40 mIU/mL and estradiol concentration ≤ 110 pmol/L within the 6 months prior to study drug administration.
- 12. Positive serum pregnancy test at screening or on Day -1.
- 13. Serum creatinine greater than the upper limit of normal (ULN) of the reference range of the testing laboratory at screening or on Day –1.
- 14. Alanine aminotransferase (ALT) or aspartate aminotransferase (AST) > ULN of the reference range of the testing laboratory at screening or > $1.5 \times$ ULN of the reference range of the testing laboratory on Day -1.
- 15. Any of the following hematology results: hemoglobin < 130 g/L for males and < 115 g/L for females, hematocrit < 0.37 L/L for males and < 0.33 L/L for females, white blood cell (WBC) count < $3.0 \times 10^3/\mu$ L, absolute neutrophil count < $2.0 \times 10^3/\mu$ L, and platelet count < 150 or > 400 × 10³/\muL at screening or on Day –1. Complete blood count (CBC) clinical laboratory results that are considered clinically relevant and unacceptable by the investigator at Day –1.
- 16. History of complement deficiency or complement activity below the normal reference range as evaluated by CAP ELISA at screening.
- 17. History of malignancy with the exception of a nonmelanoma skin cancer or carcinoma in situ of the cervix that has been treated with no evidence of recurrence.

- 18. Participation in a clinical study within 30 days before initiation of dosing on Day 1 or use of any experimental small-molecule therapy within 30 days prior to dosing on Day 1.
- 19. Participation in more than one clinical study of an mAb, or participation in a clinical study of an mAb within the 12 months prior to screening, during which the subject was exposed to the active study drug. Subjects who have participated in only one study of a mAb may be considered for enrollment if they completed that study more than 12 months prior to screening.
- 20. Prior exposure to ALXN1210.
- 21. Major surgery or hospitalization within 90 days prior to dosing.

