12.5. Administration

12.5.1. Administration of ALXN1210 SC and Placebo SC

All doses of ALXN1210 SC or placebo SC will be administered by four 100-mg SC injections of 1 mL each (Table 7) in the abdominal area. All four 1-mL injections should be administered over a 15-minute period, and there should be at least 15 minutes between the end of injection in one subject and the start of injection in the next subject.

Cohort	Study drug and dose	Number of 1-mL syringes prepared	Total volume administered
1a	1 dose of 400 mg ALXN1210 SC or placebo SC	4	4 mL
1b	1 dose of 400 mg ALXN1210 SC or placebo SC	4	4 mL

Table 7: Dosing Reference Chart for ALXN1210 SC and Placebo SC Preparation

For further information regarding the preparation and administration of study drug, please see the pharmacy manual. Please refer to the SOM for additional information regarding blinding and study drug administration.

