13. PHARMACOKINETIC AND PHARMACODYNAMIC ASSESSMENTS

13.1. Serum Sample Collection

The total anticipated volume of serum collected per subject for clinical laboratory, PK, PD, and immunogenicity assessments will not exceed 500 mL per subject. Please refer to the laboratory manual for specific details regarding serum volumes.

After study drug administration, serum samples for the determination of serum ALXN1210 concentrations and for analyses of total and free C5 concentrations, cRBC hemolysis, and potentially other measures of C5 activation will be collected at the following time points, with the actual serum sampling dates and times being recorded and used in the PK and PD calculations:

Serum concentrations of ALXN1210 will be assayed from the following sampling time points: pre-dose (within 15 minutes prior to start-of-infusion/injection [SOI]); Day 1 at end of infusion/injection (EOI), 30 minutes post EOI, and the following time points following SOI: 2 h, 4 h, and 8 h; Day 2 (24 h); Day 3 (48 h); Day 5 (96 h); Day 8 (168 h); Day 15 (336 h); Day 22 (504 h); Day 29 (672 h); Day 36 (840 h); Day 43 (1008 h); Day 50 (1176 h); Day 57 (1344 h); Day 71 (1680 h); Day 90 (2136 h); Day 120 (2856 h); Day 150 (3576 h); and Day 200 (4776 h).

Please refer to the SOM for the time windows for collection, and to the laboratory manual for details on sample collection, including the serum volume requirements.

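### Does the rule on two successive BLQ values in SAP 4.5 discard an SC profile that begins with two BLQ samples?

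*SAP*

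**What the plan says.** SAP 4.5 gives four BLQ rules for deriving PK parameters, in this order:

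1. **Leading values.** "If a Below the Level of Quantitation (BLQ) value occurs in a profile before the first measurable concentration", it is set to zero.
2. **Embedded values.** A BLQ value after a measurable one and followed by a quantifiable one is omitted, after visual inspection of the profile.
3. **End of profile.** A BLQ value after the last quantifiable concentration is treated as missing.
4. **Two in a row.** "If 2 BLQ values occur in succession, the profile will be deemed to have terminated at the first BLQ value and any subsequent concentrations" are omitted from the PK calculations.

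A separate sentence covers means and medians at each time point: "all BLQ values will be set to zero except when an individual BLQ falls between 2 quantifiable values".

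SAP 4.9 refers missing and BLQ values back to Section 4.5. SAP 4.5.1 then uses Cmax, AUCt and AUC∞ for the SC/IV geometric mean ratios.

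On sampling, Protocol 13.1 lists pre-dose and then "Day 1 at end of infusion/injection (EOI), 30 minutes post EOI". Table 4 of Protocol 9 adds that "EOI will be approximately 15 minutes after SOI", and Protocol 12.5.1 says that "All four 1-mL injections should be administered over a 15-minute period". Protocol 10.2 excludes subjects with "Prior exposure to ALXN1210".

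**The concern.** Rules 1 to 3 each state a position in the profile. Rule 4 does not, and no order of precedence is given. Two leading BLQ values therefore satisfy both rule 1, which sets them to zero and keeps the profile, and the bare words of rule 4, which end the profile at the first of them.

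The case is not far-fetched. Pre-dose should be BLQ in everyone, because earlier exposure is an exclusion. The next sample is taken as the last SC injection is completed, when little drug may have been absorbed. IV subjects have received the full dose by then, so the problem would fall almost entirely on the SC arm, the numerator of the primary bioavailability ratio. An SC subject handled literally would have no Cmax, AUCt or AUC∞ and would drop out of the PK population.

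**Working it through.** The plan states no figure on this point. The check has three parts.

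**1. How much is lost under each reading**

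Protocol 13.1 schedules 22 PK samples: pre-dose; EOI, 30 minutes after EOI, 2, 4 and 8 h (5 samples); and 24 h to 4776 h (16 samples). Post-dose samples: 5 + 16 = 21.

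- Rule 4 applied to leading values: the profile ends at pre-dose and 21 post-dose samples are dropped. EOI is itself BLQ in this case, so at most 20 quantifiable values are lost.
- Rule 1 applied: none is lost.

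**2. Whether the case can be shown to arise**

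Inputs from the documents: 400 mg SC as four 100-mg injections over 15 minutes; F = 0.6 (SAP 4.2: "assuming an absolute bioavailability of 0.6"); half-life 30.8 days (Protocol 8.3.1), so ke = 0.693/30.8 = 0.0225 per day.

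Assumed, not in the documents: absorption rate ka 0.1 to 1.0 per day, volume V 3 to 8 L, one compartment, no lag, injections at 0, 5, 10 and 15 minutes.

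C(EOI) = Σ F·100·ka / [V(ka − ke)] · (e^(−ke·t) − e^(−ka·t)), with t = 15, 10, 5 and 0 minutes.

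For such short times this is close to 60·ka·Σt/V, with Σt = 30 min = 0.0208 day:

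- Lowest (ka 0.1, V 8): 60 × 0.1 × 0.0208/8 = 0.016 µg/mL
- Middle (ka 0.2, V 5): 60 × 0.2 × 0.0208/5 = 0.050 µg/mL
- Highest (ka 1.0, V 3): 60 × 1.0 × 0.0208/3 = 0.417 µg/mL (0.415 with the full formula)

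With all four injections at time 0 the range is 0.031 to 0.829 µg/mL. A lag would lower every value. For IV, C(EOI) is about 400/V, or 50 to 133 µg/mL, which is about 320 (ka 1.0) to 3,200 (ka 0.1) times the SC value at the same V.

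A second set of assumptions (V 5 L, half-life 31 days, the whole dose at time 0) gives:

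| Absorption half-life | SC concentration at EOI |
|---|---|
| 24 h | 0.345 µg/mL |
| 48 h | 0.173 µg/mL |
| 72 h | 0.115 µg/mL |

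With an assay limit of 0.05 or 0.1 µg/mL, no profile starts with two BLQ values. At 0.25 the two slower ones do, and at 0.5 or above all three do. The answer depends on figures the documents do not give.

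**3. Which reading the section supports**

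- Rule 1 is written for leading values and does not limit how many there may be. Rule 4 is general. The specific rule governs its own case.
- Rule 4 comes straight after the end-of-profile rule and says the profile has terminated. Before the first measurable concentration there is nothing to terminate.
- Rule 4 has a clear task in the tail. Rule 2 deals with an isolated embedded BLQ value, and rule 4 deals with two together followed by a stray quantifiable value.
- The rule for means and medians also sets leading BLQ values to zero.
- AUCt runs to the last quantifiable concentration and Cmax is the maximum observed. A profile ended at pre-dose has neither.

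Under this reading the second set of profiles keeps 20 to 22 of 22 points at assumed limits from 0.05 to 2 µg/mL. The zeros themselves cost almost nothing: with a 24-h absorption half-life and a limit of 0.5 µg/mL, AUCt is 51,257.18 instead of 51,257.31 µg·h/mL.

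**The case for a change.** The best argument for a change is that a prespecified rule feeding a primary endpoint should not need interpretation. SAP Section 1 gives the PK calculations to the sponsor or its designee and the statistical analyses to another organisation, so the text has to carry its meaning between groups. The sentence on means and medians governs summary concentrations and does not formally settle parameter derivation. The definition of AUCt is not conclusive either, since in the tail rule 4 deliberately drops later quantifiable values. The remedy would be one clause, with no effect on data or sample size.

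What stands is that the qualifier is missing and that adding it would do no harm. What does not stand is that the result is at risk. The literal reading requires an analyst to set aside the rule written for exactly this situation and to accept a profile with no measurement in it. Such an outcome would also be visible. SAP 4.5 lists every concentration by subject, and SAP 4.1 settles membership of the PK population at the Blind Data Review Meeting before database lock. SAP 4.5 further requires the study report to explain parameters that could not be estimated. An SC subject with up to 20 quantifiable concentrations and no AUC would be hard to overlook.

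**Conclusion.** No change follows. This is a missing qualifier that any PK analyst would supply from the rest of the section. Under that reading no sample is lost and the SC/IV ratios for Cmax, AUCt and AUC∞ are unaffected. The loss of 21 post-dose samples per affected subject belongs only to a reading that the section itself argues against. The number of affected subjects cannot be estimated: under the assumed ka, V and injection timing, with no lag, the typical SC concentration at EOI lies anywhere from about 0.016 to 0.83 µg/mL, and the assay limit is not stated. The conclusion does not depend on those assumptions, because the leading-value rule keeps the profile whether or not the EOI sample is BLQ.
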